#### **Study Schedule/Procedures:**

Subjects will have regularly scheduled study visits at the clinical site as part of a 28-day cycle. Study visits are as follows:

- Screening: Day -28 through Day -1
- Cycle 1: Day 1, 4, 8, 11, 15, 22
- Subsequent cycles: Day 1 ( $\pm$  2 days; note that Day 1 must be a day with INCB059872 treatment) and Day 15 ( $\pm$  2 days)
- End of treatment: Subjects must be seen and have blood drawn 2 times per week for 2 weeks after last dose.
- Safety follow-up: 30 days (+ 5 days) after the EOT visit or last dose of study drug if EOT visit not performed (or until toxicities resolve, return to baseline, are deemed irreversible, or the subject receives another anticancer therapy, whichever is shorter).

- Follow-up for disease status (only for subjects who discontinue for reasons other than disease progression).

Laboratory tests for safety

Study visits will include sample collection for hematology, chemistry, coagulation, lipid panel, and urinalysis. Additionally, the screening visit will include serology and fertility/pregnancy testing.

Laboratory tests for PK

Pharmacokinetic [REDACTED] samples will be collected at planned visits and shipped to the sponsor or designee for analysis.

Clinical assessments

Adverse event assessments, vital signs, ECG, physical examination, ECOG performance status, and disease response assessments will be performed by the investigative site.

An objective assessment of disease status will be performed as screening, appropriate to the malignancy type (eg, CT or MRI, bone marrow biopsy/aspirate, peripheral blood, as applicable by tumor type).

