#### 4.1.1. Monotherapy Dose Escalation (Part 1)

Approximately 24 subjects will be enrolled into each dose-escalation treatment group.

Treatment Group A will enroll subjects with AML or MDS. The enrollment in TG B is prioritized for SCLC. Enrollment of subjects with other solid malignancies (eg, endocrine tumors) is allowed with the sponsor medical monitor approval.

Dose escalation for TG A and TG B in Part 1 will proceed independently, with each treatment group following a 3 + 3 design. The starting dose of INCB059872 for TG A and TG B will be 2 mg QOD. A minimum of 3 subjects will initially be enrolled in each treatment group in Part 1, and each subject will be observed for a DLT observation period of 1 cycle (28 days) before the next dose cohort begins enrollment. Subjects must have taken at least 75% of the cohort-specific dose (at least 11 doses for QOD schedule or at least 21 doses for QD schedule) in the first 28 days of study treatment or have had a DLT to be considered evaluable. Subjects who are not evaluable will be replaced. The dose will be escalated by up to 100% if none (0) of the first 3 evaluable subjects enrolled has a DLT. Dose escalation should proceed in smaller increments (ie, by no more than 50%) if a DLT is observed, or if 2 or more subjects at a given dose level experience Grade 2 or higher AEs (unless they are clearly and incontrovertibly due to an alternative cause).

If 1 of the first 3 evaluable subjects enrolled has a DLT, the cohort will be expanded to include 3 additional evaluable subjects, and if no DLT occurs in the additional 3 subjects, then the dose will be escalated by up to 100%. Otherwise, if 2 subjects in a cohort of 3 or 6 subjects experience DLTs, the MTD will be deemed to be exceeded. An interim lower dose level may be explored if the dose increment has been 100%. The MTD will be defined as 1 dose level below

the dose level at which one-third or more subjects experience DLTs. Upon the aggregate review of overall safety, PK, [REDACTED] and efficacy, a recommended dose (per tumor type) will be determined to maximize the clinical benefit/risk margin.

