### 5.4.3. Dose-Limiting Toxicity and Determination of Maximum Tolerated Dose of INCB059872

Dose-limiting toxicity will be defined as the occurrence of any of the toxicities in Table 4 occurring up to and including Day 28, except those with a clear alternative explanation (eg, disease progression) or transient ( $\leq$  72 hours) abnormal laboratory values without associated clinically significant signs or symptoms based on investigator determination. All DLTs will be assessed by the investigator using CTCAE v4.03 criteria (NCI 2010). Subjects who receive at least 75% of the planned doses (eg, 11 of 14 doses for QOD schedule) of study drug at the level assigned or have a DLT will be considered evaluable for determining tolerability of the dose. Subjects who cannot complete 75% of the planned doses of study drug for reasons not due to toxicities related to study drug will not be considered evaluable for the purposes of determining the MTD and will be replaced.

Individual subject dose reductions may be made based on events observed at any time during treatment with study drug; however, for the purposes of dose cohort escalation/de-escalation, expanding a dose cohort, and determining the MTD of INCB059872, decisions will be made based on events that are observed from the first day of study drug administration through and including the final day of Cycle 1 (Day 28). A lower MTD may subsequently be determined based on relevant toxicities that become evident after Day 28.

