**Table 8: Schedule of Laboratory Assessments**

Local Laboratory Tests	Protocol Section	Screening	Treatment						EOT	Safety Follow-Up	Notes			
			Cycle 1			Cycles 2+								
			Day 1	Day 8 (± 2 Days)	Day 15 (± 2 Days)	Day 22 (± 2 Days)	Day 1 (± 2 Day)	Day 15 (± 2 Days)						
Serum chemistries	Table 9	X	X*	X	X	X	X	X	X	X	* May be performed 3 days before the first dose.			
Hematology*	Table 9	X	X**	X	X	X	X	X	X***	X	* Must be drawn twice a week for the first 2 weeks of study treatment. In addition to Cycle 1 Day 1 and Cycle 1 Day 8, hematology samples should be drawn at Cycle 1 Day 4 ± 1 day and Cycle 1 Day 11 ± 1 day. ** May be performed 3 days before the first dose. *** Must be drawn twice a week for 2 weeks after last dose.			
Lipid panel	Table 9	X	X	X	X	X	X	X	X	X				
Coagulation panel	Table 9	X					X*		X		* Cycle 2 Day 1 and then every 3 cycles thereafter.			
Hepatitis screening	Table 9	X												
Urinalysis	Table 9	X					X*				* Cycle 2 Day 1 and then every 3 cycles thereafter			
Pregnancy test	Table 9	X*	X**						X**		All female subjects of childbearing potential. * Serum ** Urine			
PK plasma (predose)	7.8.1		X	X	X	X	X*				Collect before morning dose of study drug. * Cycle 2 Day 1, only for food-effect testing in Part 2.			
PK plasma TIMED (postdose)	7.8.1.1		X*		X*		X**				* Collect at 0.5, 1, 2, 4, and 6 hours after INCB059872 dose. Excess sample will be used for [redacted] analysis. ** Cycle 2 Day 1 only for food-effect study.			

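### Protocol 5.4.3 dates DLTs both by occurrence and by observation through Day 28, and Table 8 guarantees no laboratory draw between the Day 22 visit and Cycle 2 Day 1, so a late laboratory-only DLT may go uncounted

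*Protocol*

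**What the plan says.** Section 5.4.3 of the protocol contains two rules. The definition covers "toxicities in Table 4 occurring up to and including Day 28". The decision rule rests escalation, de-escalation, cohort expansion and the MTD on "events that are observed from the first day of study drug administration through and including the final day of Cycle 1 (Day 28"). The section then adds: "A lower MTD may subsequently be determined based on relevant toxicities that become evident after Day 28".

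On timing, Section 4.1.1 says "each subject will be observed for a DLT observation period of 1 cycle (28 days) before the next dose cohort begins enrollment", and Section 4.1.3 has a matching sentence for Part 3. Section 4.1.2 stops enrolment to a Part 2 cohort if 5 or more of the first 15 subjects have DLTs during Cycle 1.

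The Synopsis visit list reads "Cycle 1: Day 1, 4, 8, 11, 15, 22". Table 8 concentrates the extra hematology early: "Must be drawn twice a week for the first 2 weeks of study treatment". It specifies: "In addition to Cycle 1 Day 1 and Cycle 1 Day 8, hematology samples should be drawn at Cycle 1 Day 4 ± 1 day and" on Day 11 ± 1 day. Chemistry is drawn on Days 1, 8, 15 and 22. The Day 22 visit and Cycle 2 Day 1 each carry a ±2-day window. For Day 1 of later cycles the Synopsis adds: "note that Day 1 must be a day with INCB059872 treatment".

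In Table 4, any Grade 4 thrombocytopenia is a DLT in solid tumors, with or without symptoms. In AML, MDS and MF the platelet DLT requires clinically significant bleeding or a transfusion requirement outside institutional practice. SAP Section 9.2.2 lists DLTs for Parts 1 and 3 only.

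**The concern.** A laboratory abnormality without symptoms is observed when blood is drawn. On the nominal schedule the last draw inside the window is on Day 22 and the next is on Day 29, one day after the window closes. If a Grade 4 platelet count is first found on Day 29, its onset date is unknown and its observation date is late. The definition sentence would let it be judged a Cycle 1 event. The decision sentence, read as written, would not.

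The toxicity concerned is the one this drug has shown. Section 1.6.2 reports six DLTs of Grade 3 or higher thrombocytopenia or platelet count decrease, all in TG B (1 + 2 + 3 across three cohorts). Any miscount would run towards fewer DLTs. That favors escalating, or passing a dose as tolerated, in Part 3, and continuing enrolment in Part 2. The counting consequence is clearest in TG B1 and B2 (the Part 2 rule) and TG E (the 3 + 3 count). TG E1 has the same draw schedule, but Section 4.1.4 states no DLT-count rule for it.

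**Working it through.** **1. The schedule.** Scheduled hematology days (Synopsis, Table 8) are 1, 4, 8, 11, 15, 22 and then 29 nominally. The gaps are 3, 4, 3, 4, 7 and 7 days. The last gap leaves Days 23 to 28, six days, without a scheduled count.

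**2. The visit windows.** The Day 22 visit may fall on Days 20 to 24 and Cycle 2 Day 1 on Days 27 to 31, giving 5 × 5 = 25 permitted pairs. The uncovered tail is 28 minus the last draw day that is not later than Day 28.

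| Cycle 2 Day 1 falls on | Pairs | Days uncovered up to Day 28 |
|---|---|---|
| Day 27 | 5 | 1 |
| Day 28 | 5 | 0 |
| Day 29, 30 or 31 | 15 | 4 to 8 (28 − 24 to 28 − 20) |

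So 10 of 25 pairs put a draw inside the last two days of the window, and 15 of 25 do not. With uninterrupted alternate-day dosing from Day 1 and the rule that Cycle 2 Day 1 is a dosing day, only Days 27, 29 and 31 are available. Then 5 of 15 pairs are covered to within a day. These are counts of permitted combinations, not probabilities.

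**3. The plan's own figure.** For a DLT rate p, P(escalate) = (1 − p)³ + 3p(1 − p)² × (1 − p)³. At p = 0.30 this is 0.343 + 0.151 = 0.494, the 49.4% in Table 11. The other five rows also reproduce (90.6, 70.9, 30.9, 17.2 and 8.2%).

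**4. Illustration of undercounting.** Assume that a fraction f of DLTs is not counted, so the 3 + 3 acts on p(1 − f). The documents give no value for f. The 6/28 row takes onset as uniform over 28 days and loses every event of Days 23 to 28. The 3/28 row loses half of them.

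| f | Rate acted on at true 30% | P(escalate), true 30% | P(escalate), true 40% |
|---|---|---|---|
| 0 | 30.0% | 49.4% | 30.9% |
| 1/28 | 28.9% | 51.6% | 33.3% |
| 3/28 | 26.8% | 56.2% | 38.3% |
| 6/28 | 23.6% | 63.1% | 46.5% |
| 8/28 | 21.4% | 67.8% | 52.4% |

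For the Part 2 rule, P(5 or more of 15) at a true 30% is 48% with f = 0, 37% with f = 3/28 and 27% with f = 6/28.

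**The case against.** The strongest reply is that Section 5.4.3 defines a DLT by occurrence, so a Grade 4 count in the pre-dose Day 29 sample can be judged to have arisen in Cycle 1. Other provisions favor that reading. Section 5.4.3 exempts symptom-free laboratory abnormalities lasting 72 hours or less. In Table 4, solid-tumor neutropenia turns on recovery within 7 days of interruption, and AML/MDS/MF neutropenia on a duration of at least 6 weeks. A strict observed-by-Day-28 rule would make these partly or wholly unusable. This stands. It shows that the two sentences conflict, but does not say which one governs the count.

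Other points also stand in part:

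- In AML, MDS and MF a platelet DLT needs bleeding or a transfusion requirement, which can present between visits. The gap therefore bears mainly on solid tumors.
- Table 5 has solid-tumor subjects held and monitored at platelets of 25 to below 50 × 10⁹/L, so a subject already falling at Day 22 should have repeat counts. If Grade 4 means below 25 (an assumption, matching Table 5's lower band), what escapes is a drop from at least 50 to below 25 between visits.
- TG E starts at the monotherapy recommended dose and may not exceed the monotherapy MTD, so upward escalation matters less there. The same tally would still bear on whether the dose is passed as tolerated.
- Cohort calls adjudicate high-grade events (Section 5.4.6), decisions follow data review (Section 8.7), and the MTD may be lowered later. These safeguards are discretionary, and none puts a late-found event into the 3 + 3 or Part 2 count.

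A reader might infer that every laboratory DLT of Days 23 to 28 is first seen after the window and lost, so that the window is in effect 22 days. The documents do not support that. The Day 22 draw may be as late as Day 24, Cycle 2 Day 1 may be on Day 27 or 28, unscheduled counts are not barred, and the occurrence wording allows such an event to be counted.

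**Conclusion.** The point holds as an unreconciled rule combined with a gap in guaranteed ascertainment. Section 5.4.3 leaves open whether an abnormality first found at Cycle 2 Day 1 counts. In 15 of 25 permitted visit combinations, the last 4 to 8 days of the window have no scheduled laboratory draw. Following the observed sentence literally can only lower the DLT count.

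The size of the effect cannot be fixed from the documents. At a true 30% rate, P(escalate) of 52% to 63% against 49.4% is an illustrative range. The 63%, and the matching 27% for the Part 2 rule, are upper-end values: they treat all DLTs as laboratory-only, take onset as uniform and miss every event of Days 23 to 28. Onset concentrated late in the cycle would enlarge the effect, and early onset would shrink it. A reader might also infer that Table 11 is wrong. It is not: its arithmetic is exact, conditional on every DLT in the window being ascertained.

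The change should be made, because the undercount is one-directional, concerns the drug's main observed toxicity, and can be closed with a draw already scheduled.

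**What to change.** 1. In Section 5.4.3, reconcile the two sentences so that attribution is by occurrence through Day 28.
2. State there, and carry into Sections 4.1.1 to 4.1.3, that the pre-dose Cycle 2 Day 1 laboratory results are part of Cycle 1 DLT ascertainment. An abnormality first found in them is adjudicated at cohort review as a possible Cycle 1 event unless its onset is shown to be after Day 28. Counting every result up to Day 31 automatically would go too far, because it would bring in events that arose after the window.
3. Do not close cohort review until those results are in.
4. In SAP Section 9.2.2, program the DLT listing on the same rule and extend it to the Part 2 stopping-rule count.

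The cost is a few sentences in the protocol and SAP and no added visit or draw. Cohort review moves by about 1 to 3 days, and slightly more DLTs may be counted.

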**Table 4: Definition of Dose-Limiting Toxicity**

Nonhematologic toxicity

Any <math>\geq</math> Grade 3 nonhematologic toxicity EXCEPT:

Transient (<math>\leq</math> 72 hours) abnormal laboratory values without associated clinically significant signs or symptoms.

Nausea, vomiting, and diarrhea adequately controlled with medical therapy within 48 hours.

An event clearly associated with the underlying disease, disease progression, a concomitant medication, or comorbidity.

Singular or nonfasting elevations in blood glucose (ie, blood glucose excursions will be considered toxicities if fasting blood glucose is elevated on 2 separate occasions).

Hematologic toxicity

Anemia : Grade 4, unexplained by underlying disease

Neutropenia:

For solid tumors: Grade 4 that does not recover to <math>\leq</math> Grade 3 in <math>\leq</math> 7 days after dose interruption.

For AML/MDS/MF: Grade 4 with a hypocellular bone marrow lasting <math>\geq</math> 6 weeks after the start of a course in the absence of residual disease.

Febrile neutropenia (for solid tumors only): absolute neutrophil count <math>< 1.0 \times 10^9/L</math> with a single temperature of <math>> 38.3^\circ C</math> (<math>101^\circ F</math>) or a sustained temperature of <math>\geq 38^\circ C</math> (<math>100.4^\circ F</math>) for more than 1 hour.

Thrombocytopenia:

For solid tumors: Any Grade 4 or Grade 3 with bleeding or any requirement of platelet transfusion.

For AML/MDS/MF: Grade 3 or higher with clinically significant bleeding or any requirement of platelet transfusion outside of institutional practice.

Other toxicities not meeting criteria above

While the rules for adjudicating DLTs in the context of dose escalation are specified above, an AE not listed above may be defined as a DLT after a consultation with the sponsor and investigators, based on the emerging safety profile.

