#### **5.4.6. Procedures for Cohort Review and Dose Escalation**

Telephone conferences will be scheduled by the sponsor with study investigators in order to review cohort-specific data and overall safety data, to agree on dose escalation, adjudicate individual high-grade AEs as potentially dose-limiting, and guide other major study decisions.

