## 8.7. Data Monitoring Committee

No independent Data Monitoring Committee is planned for this study. Decisions to continue the enrollment in subsequent dose level cohort, dose level to be tested, as well as number of subjects to be evaluated, will be made after the appropriate data are collected and reviewed by sponsor representatives (eg, medical monitor) and investigators or designees. The group of sponsor representatives and investigators or designees will convene regularly (eg, once weekly) or ad hoc for specific discussions. Meeting minutes will be documented.

An internal Data Safety Monitoring Board (iDSMB) will review safety data at regular intervals throughout the study. The frequency of meetings will be contingent upon enrollment and availability of safety data for analysis and review. Details regarding membership, roles, and responsibilities of the committee are specified in the iDSMB charter.

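### In TG C and TG D (Part 3), the only listed neutropenia DLT for AML/MDS cannot be met before about Day 42, but 3 + 3 and MTD decisions use events through Day 28, so it enters the count only by discretion

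*Protocol*

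**What the plan says.** - **Criterion.** Protocol Table 4 has one neutropenia row for AML/MDS/MF: Grade 4 with a hypocellular marrow, persisting for at least "6 weeks after the start of a course in the absence of residual disease". The febrile neutropenia row is for solid tumors only.
- **Window.** Section 5.4.3 opens: "Dose-limiting toxicity will be defined as the occurrence of any of the toxicities in Table 4 occurring up to and including Day 28". It then bases escalation, de-escalation, cohort expansion and the MTD on "events that are observed from the first day of study drug administration through and including the final day of Cycle 1 (Day 28").
- **Part 3.** Section 4.1.3 uses a 3 + 3 design in TG C (with ATRA) and TG D (with azacitidine). Each subject is observed for one 28-day cycle before the next cohort or Part 4 opens.
- **Routes for later events.** Section 5.4.3 adds: "A lower MTD may subsequently be determined based on relevant toxicities that become evident after Day 28". Table 4 ends with a catch-all under which "an AE not listed above may be defined as a DLT after a consultation with the sponsor and investigators". Section 5.4.6 has calls that "adjudicate individual high-grade AEs as potentially dose-limiting". Section 8.7 says enrollment and dose decisions "will be made after the appropriate data are collected and reviewed by sponsor representatives" and investigators.
- **SAP.** Section 9.2.2 only lists DLTs for Parts 1 and 3. It adds no timing rule.

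**The concern.** A safety criterion written for dose-finding does not operate in the step it was written for. Neutropenia is among the main toxicities the protocol names for INCB059872 (Section 1.6.1), and myelosuppression is given as the primary DLT of azacitidine (Section 1.6.4), so TG D is the most exposed group. Both combinations start at 2 mg QD, two levels below the monotherapy dose of 4 mg QD, so upward steps are foreseen, followed by Part 4 cohorts of about 30 subjects. A dose could be escalated, or carried into Part 4, while a case of prolonged marrow aplasia at that dose is still unconfirmed and absent from the count.

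**Working it through.** **1. The plan's own figure.** Protocol Table 11 (SAP Table 1) gives the probability of escalating at true DLT rate p. For a 3 + 3:

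P(escalate) = (1−p)³ + 3p(1−p)² × (1−p)³ = (1−p)³ + 3p(1−p)⁵

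At p = 0.10: 0.729 + 0.3 × 0.59049 = 0.906. For p = 10% to 60% the formula gives 90.61, 70.86, 49.43, 30.93, 17.19 and 8.24%, which matches the table at all six rates.

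**2. Timing.** A course cannot start before Cycle 1 Day 1. Six weeks is 6 × 7 = 42 days, so the criterion is first met at about Day 42 (Day 43 if counted as Day 1 + 42). The cutoff is Day 28, and 42 − 28 = 14 days. Whatever the true rate of the event, its contribution to a count closed at Day 28 is zero.

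**3. What one event changes.** In a 3 + 3, one extra DLT turns 0 of 3 (escalate) into 1 of 3 (enroll three more), or 1 of 6 (escalate) into 2 of 6 (MTD exceeded).

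**4. Illustrative size.** The documents give no rate for this event, so a = 2% and 5% are assumptions, as are the rates of other DLTs, o = 10% and 20%. Independent: p = 1 − (1−o)(1−a). Half overlap (half of the aplasia subjects already have a counted DLT): p = o + a/2. Full overlap: p = o, so no difference.

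| o | a | P(escalate) now | If counted, independent | If counted, half overlap |
|---|---|---|---|---|
| 10% | 2% | 90.6% | 87.5% (p = 0.118) | 88.9% (p = 0.110) |
| 10% | 5% | 90.6% | 82.4% (p = 0.145) | 86.2% (p = 0.125) |
| 20% | 2% | 70.9% | 67.4% (p = 0.216) | 68.7% (p = 0.210) |
| 20% | 5% | 70.9% | 62.2% (p = 0.240) | 65.4% (p = 0.225) |

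The gap is 3.1 to 8.7 points under independence, 1.7 to 5.5 with half overlap, and nil with full overlap. Myelosuppressive toxicities are likely to be positively correlated, so the independent column is near an upper bound.

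**5. How often the question would arise.** The chance of at least one such event is 1 − (1−a)ⁿ. For n = 3 it is 5.9% at a = 2% and 14.3% at a = 5%. For n = 6 it is 11.4% and 26.5%.

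**The case against.** The best textual reply is that neutropenia starting in Cycle 1 occurs within the window and only its duration is pending. Grade 4 counts and a hypocellular marrow can both be seen by Day 28, and 28 days is a minimum wait, not an order to open the next cohort on Day 29. This does not rescue the rule. Section 5.4.3 ties decisions to what has been observed by Day 28, at which point the event is not yet a DLT, and nothing requires a cohort to wait for a pending case.

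The second reply is that late toxicity is provided for by a possible lower MTD, the catch-all, the review calls and the wait for appropriate data. These routes exist, so a reader should not infer that prolonged aplasia can never affect the dose. None has a threshold or a required wait, however, and the catch-all fits poorly because it covers events not listed, whereas this one is.

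The third reply is about size, and much of it stands. The rates are assumed. Section 1.6.2 reports no DLTs in 17 TG A subjects up to 4 mg QD, and Part 3 may not exceed the monotherapy MTD. That reassurance is partial: if the same row and window applied in TG A, this event could not have been counted by rule there either. Section 1.6.1 calls the main toxicities clinically manageable, and Section 1.6.4 calls azacitidine's hematologic toxicities reversible.

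The objection also stands against a broad remedy. AML/MDS subjects have no lower neutrophil limit at entry (Section 3.2, criterion 4), so holding cohorts for any Grade 4 neutropenia ongoing at Day 28 would stop many of them. If 10, 30 or 50% of subjects triggered the hold (assumed), 1 − (1−r)³ gives 27, 66 or 88% of 3-subject cohorts. The trigger must be narrower. Finally, Cycle 2 azacitidine may start at about Day 29 and blur a Day 42 assessment; that has to be weighed case by case.

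**Conclusion.** The point holds for TG C and TG D in Part 3: followed as written, the listed neutropenia criterion for AML/MDS cannot enter the 3 + 3 count, and only discretion can bring it in. This rests on the text and the 14-day gap, not on any assumed rate. The size is unknown and probably small. Grade 4 anemia unexplained by disease, thrombocytopenia with significant bleeding or unusual transfusion need, and Grade 3 or higher infection not clearly due to disease or another listed exception still count by Day 28. Hematology and iDSMB review also continue.

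Four stronger readings are not supported:

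- **The Part 2 stopping rule also fails.** Section 4.1.2 counts DLTs in Cycle 1 cumulatively and sets no Day 28 decision point. An event with Cycle 1 onset confirmed at week 6 could be counted; the text is merely silent.
- **The TG A dose is undermined.** It has already been selected, and the documents report no such event there.
- **Omitting febrile neutropenia for hematologic tumors is an oversight.** Appendix K (Amendment 2) records it as deliberate.
- **Subjects held for neutropenia are meant to be replaced.** Section 5.4.3 says that those who miss doses "for reasons not due to toxicities related to study drug will not be considered evaluable for the purposes of determining the MTD". Sections 4.1.3 and 4.3.2 omit that limit, which is a secondary wording difference.

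**What to change.** In Section 5.4.3, and by reference in Section 4.1.3, keep the 28-day window for all other DLTs and add a pending category for AML/MDS subjects. A subject is pending if the Grade 4 neutropenia:

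1. was absent at baseline;
2. began in Cycle 1;
3. is ongoing at Day 28; and
4. has a hypocellular marrow without residual disease, on a marrow done as clinically indicated (Section 7.6).

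Follow that subject to Day 42. If confirmed, count the event as a DLT at that dose level and re-apply the escalation and MTD decision with the updated count. Escalation above that level, or opening Part 4 at it, waits only for subjects who meet this definition.

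In Section 4.1.2, state that an event with Cycle 1 onset confirmed at week 6 counts in the Part 2 stopping rule.

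Separately, align Sections 4.1.3 and 4.3.2 with Section 5.4.3 on replacement. Table 5 tells sites to hold INCB059872 for suspected drug-related neutropenia, and on QD dosing a hold of 8 or more days leaves at most 28 − 8 = 20 doses, below the 21 required. The text should say whether such a subject without a DLT is evaluable; alignment alone does not settle that.

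**Cost.** A text amendment and up to about 14 days' delay in the few affected cohorts. The criterion already needs marrow evidence, and Section 7.6 strongly encourages a marrow around Cycle 2 Day 1 in subjects with a marked fall in circulating blasts, though a further marrow near Day 42 may be needed. Because the trigger depends on a clinically indicated marrow, a subject without one would not become pending. That is the price of avoiding routine holds.
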